### Psilocybin-Assisted Therapy

The participant will attend 1 preparatory session that occurs within 7-days of the first psilocybin dosing session (V3) to develop a therapeutic alliance, set intentions for the experience, and learn what to expect during the dosing session. In addition, the participant will undergo 2 integrative therapy sessions after the intervention (V5 & V6). Each therapist will undergo training with the study investigator and using the principles outlined in the Yale Manual for Psilocybin-Assisted Therapy of Depression (DOI: 10.31234/osf.io/u6v9y).

These include:

- Preparatory sessions to establish rapport & therapeutic alliances with the participant & study therapist
  - In addition, providing psychoeducation for the participant to set expectations for the dosing sessions
- Providing an appropriate setting for the dosing sessions
- Maintaining a non-intrusive presence
- Responding to invitations to talk
- Responding to intense affective/emotional states
- Responding to agitation or restlessness
- Responding to requests for contact (appropriately & within the participant's boundaries)
- Follow-up sessions, aimed at helping the participant integrate & understand their psychedelic experience

These principles will apply to both dosing sessions (10mg & 25mg). As needed, therapy sessions could be paced more gently with clearer language & instruction (e.g. less open-ended or non-specific questions), from the therapists to be sensitive and responsive to the participant's needs & accommodations.

For a full description of each therapy session and PAT, please refer to the Yale Manual for Psilocybin-Assisted Therapy of Depression. Therapy sessions will not be video recorded. At least one of the therapists will be a clinician and will be available at all times during the dosage session to assess and manage any medical or psychiatric adverse events.

#### How the study intervention will appear

The psilocybin will be provided by Filament Health (Burnaby, British Columbia, Canada). The doses of psilocybin used in this study will be 10 mg (V3) and 25 mg (V4). The psilocybin will be administered in size 2 hydroxypropyl methyl cellulose (HPMC), white capsules.

## **5.2 Treatment Regimen**

The participant will be administered psilocybin at 2 points during the trial, both following the Baseline Visit (V2) after the participant's eligibility has been confirmed: firstly a safety dose of 10mg during V3 (Day -7), then a treatment dose of 25mg during V4 (Day 0). The procedures are outlined below:

Each participant will be assigned a treatment bottle of 1 capsule of 10mg or 25mg of psilocybin. Under the supervision of a clinician, the capsule of psilocybin will be taken orally with a glass of water. There will be no modifications to the dosage, each participant will receive the same dosage for both medications. However, if adverse effects are experienced, the study clinician may make changes to the intervention, which include therapy after each session. The study clinician may decide that participants may require more therapy sessions. In addition to the psilocybin, two study therapists trained in psilocybin-assisted therapy will be supporting the participant during the dosing session. There will be 1 therapist present at all times throughout the dosing session. The total treatment time will be between 6 to 8 hours when the acute effects of the psilocybin have passed.

## **5.3 Method for Assigning Participants to Treatment Groups**

Not applicable.

## **5.4 Administration of Study Intervention**

The IP will be prepared by the CAMH pharmacy and picked up by a trained research staff member. The IP will be given to the participant by a licensed physician who will supervise the participant. The participant will receive a capsule containing either 10mg or 25mg of psilocybin, depending on the visit. The capsules will be taken orally, with water. The capsules should not be opened or chewed.

After taking the IP, the participant will lie down on a bed in a non-clinical environment. Therapists will encourage participants to focus their attention inward and stay with any experience that arises. To enhance inward reflection, a pre-selected music playlist will be played quietly. Two study therapists trained in PAT will be supporting each participant during the dosing session with at least one therapist being present at all times to respond to the emotional and physical needs of the participant. Constant observation by therapists will monitor for adverse events during the dosing sessions. At least one member of the therapist pair will be a clinician. An on-call psychiatrist will be available at all times to further assess as needed for acute concerns.

The effects of psilocybin usually start about 20 to 30 minutes after administration, becoming the most intense in the first 90 to 120 minutes and gradually subsiding in 5 to 6 hours. The participants will be asked to remain in the room for the duration of the session regardless of the intensity of the effects, preferably lying down and mostly silent unless they have a concern or need to communicate a discomfort or seek reassurance from the therapist, or use the restroom. The therapists will 'check-in' with the participant (i.e., ask how the participant is doing) in 30-to-60 minute intervals post-dosing. A light meal and fruit will be available for the participant for lunch.

About 5 to 6 hours after dosing, the trained therapists will discuss the IP administration experience with the participant. The participant will be discharged 8 hours post-dosing when the acute effects of psilocybin are resolved (in the opinion of the investigator/therapist/study psychiatrist). The participant must be accompanied home by a caregiver who will remain with the participant for up to 24 hours after the intervention was given. The study team is to be notified that the participant has arrived home safely via phone call. In the absence of receiving a phone call, the study staff will directly contact the participant.

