At Study Visits 3 & 4 (V3/V4), participants will receive oral doses of psilocybin (safety dose of 10 mg at V3, treatment dose of 25 mg at V4), to assess the tolerability and efficacy of psilocybin. These sessions will be held one week apart and will last 6 to 8 hours each. These sessions will take place in a pre-decorated treatment room at CAMH. The sessions will be set up and led by Co-Investigator [name]. Throughout the entire duration of the dosing sessions, participants will be monitored by a minimum of two trained therapists.

At the end of each session, participants will be evaluated for safety by a study psychiatrist before being discharged. Participants will also rate the 11-Dimension Altered States of Consciousness (11D-ASC) at the end of each dosing day when the subjective effects of psilocybin have subsided to a negligible level.

Visit 5 (V5) will be held one day after administration of the treatment dose (V4). During V5 the participants will complete post-treatment clinical and cognitive assessments, alongside the second and final MRI scans (*of the main clinical trial design*). Participants will also undergo a 1-hour integration therapy session to debrief their experiences the day before. Visit 6 (V6) will be held one week following the treatment dose (V4). During V6 a second 1-hour integration therapy session takes place and all post-treatment clinical assessments will be repeated. Subsequent clinical progress will be evaluated virtually at V7, V8, V9, which will respectively be held 2, 4, and 12 weeks following the treatment session (V4). From V7-V9 the cognitive tasks and MRI will not be done for *the main clinical trial design*. A study psychiatrist will be available to respond to any concerns about changes in mental/physical states throughout the study.

Figure 1. Schematic for the Main Clinical Trial Design

Optional Sub-Study of Dense Sampling Brain MRI Collection (Section 6.1.2.2 and 6.2.2)

10 participants out of 20 participants in the main clinical trial could opt to receive 8 additional brain MRI scans besides the MRI scans at V2 and V5 required in the main clinical trial. These 8 additional scans will be assessed at V1, in the middle of medication washout/tapering period, V3, V6, V7, V8, 8 weeks following the treatment dose (V4), and

V9, respectively. At each optional MRI visit, self-rated Beck Depression Inventory-II (BDI-II) and Autistic Burnout Survey Items (ABSI) will also be collected.

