In case of development of acute anxiety or psychotic symptoms requiring pharmacological intervention, the participant will be managed under the care of the onsite psychiatrist. The participant may be discharged from the clinic when, in the opinion of the investigator, the condition has stabilized. The participant will be accompanied home. The participant is to notify the site when they have returned home safely. In the absence of receiving a phone call, site staff will directly contact the participant.

Information for how to manage subjects during difficult psychological states are detailed in the Yale Manual for Psilocybin-Assisted Therapy of Depression. All therapists will undergo training with the study investigator using this manual.

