#### ***Visit 4 (V4) – Treatment Dose / Day 0***

This intervention will occur 1 week following the safety dosing session (V3). On the day of the intervention the following procedures will take place:

- Study intervention administration (Section 5.0): 1 oral dose of 25 mg of psilocybin administered in conjunction with supportive therapy (PAT).
- Vital signs (blood pressure and pulse) will be taken every 1.5 hours during this session.
- At least one therapist will be present in the room at all times during PAT and be available to respond to participants' physical and emotional needs
- Participants will be instructed to lie on a bed in a non-clinical environment, and therapists will encourage participants to focus their attention inward and stay with any experience that arises. To enhance inward reflection, a pre-selected music playlist will be played. Administration of questionnaires or other instruments to be completed at the end of the dosing session when the acute effects of psilocybin have resolved:
  - Study team or therapist administered:
    - 11D-ASC to assess the acute drug effects.
    - UKU Side Effect Scale
- The participant will be discharged 6-8 hours post-dosing when, in the opinion of the study PI (or delegate), the acute effects of psilocybin are resolved. The participant must be accompanied home by a caregiver who will remain with them for up to 24 hours after the dose was administered.

- Rescue medications are permitted during this visit as outlined in Section 5.6.

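### The dosing-day rules conflict on discharge time (8 hours versus 6-8 hours) and on therapists present (two versus one), and leave unclear who must clear discharge

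*Protocol*

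**What the plan says.** **Time of discharge.** Section 5.4: "The participant will be discharged 8 hours post-dosing when the acute effects of psilocybin are resolved (in the opinion of the investigator/therapist/study psychiatrist". Section 6.1.2.1, Visit 4: "The participant will be discharged 6-8 hours post-dosing when, in the opinion of the study PI (or delegate), the acute effects of psilocybin are resolved". Visit 3 has the same text. The Clinical Trial Summary and sections 3.1 and 5.2 give the session or treatment time as 6 to 8 hours.

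**Therapists present.** Section 3.1, speaking of the whole length of the dosing sessions: "participants will be monitored by a minimum of two trained therapists". Section 5.2 assigns two trained therapists to support the participant, then adds: "There will be 1 therapist present at all times throughout the dosing session". Section 5.4 also assigns two and requires at least one to be present continuously. The V3 and V4 procedures require at least one in the room and do not say how many are assigned.

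**Clearing discharge.** Section 3.1: "participants will be evaluated for safety by a study psychiatrist before being discharged". Section 5.4 rests the judgement that effects have resolved on three roles joined by slashes: investigator, therapist, study psychiatrist. Section 6.1.2.1 rests it on the PI or a delegate.

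**The concern.** These are operating instructions for the hours after a psychoactive dose, and staff will work from whichever section they have open. Someone following 6.1.2.1 could discharge at 6 hours, with one therapist in the room and no psychiatrist evaluation. Someone following 3.1 and 5.4 could do none of these.

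The setting gives this weight. Section 1.4 knows of no earlier psilocybin trial in autistic people. Section 8.7 dispenses with an independent data and safety monitoring board. Section 3.2 makes the number and severity of adverse events the safety endpoint, and relies on constant therapist observation and on blood pressure and heart rate during dosing. At stake are consistent protection of participants and equal directly observed time. It is also uncertain which discharges count as deviations under section 10.2.

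**Working it through.** The protocol gives no calculated figure on this point, so the check sets the texts side by side and adds short arithmetic.

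| Rule | 3.1 | 5.2 | 5.4 | 6.1.2.1 (V3 and V4) |
|---|---|---|---|---|
| Time | session 6 to 8 h | treatment time 6 to 8 h | discharge at 8 h | discharge at 6-8 h |
| Therapists assigned | not separately stated | two | two | not stated |
| Therapists present throughout | at least two monitoring | one | at least one | at least one |
| Who evaluates or judges | psychiatrist evaluates before discharge | not stated | investigator/therapist/study psychiatrist | PI or delegate |

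**1. Time.** Eight hours lies inside 6-8 hours, so the texts agree on a discharge at 8 hours and disagree on any earlier one.
- Earliest discharge: 8 h under 5.4, 6 h under 6.1.2.1. Difference: 8 - 6 = 2 h per session.
- Share of the longer stay: 2/8 = 25%.
- Vital signs are taken every 1.5 h during each session (6.1.2.1). Counting complete intervals after the dose, a 6 h stay holds 6/1.5 = 4 sets. An 8 h stay holds 8/1.5 = 5.33, so 5 complete sets. The difference is one set.
- Section 5.4 says that effects usually subside over 5 to 6 h. For a typical participant, observed time after that is 6 - 6 = 0 h to 6 - 5 = 1 h with a 6 h discharge, and 8 - 6 = 2 h to 8 - 5 = 3 h with an 8 h discharge.

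**2. Therapists present.** Two assigned with at least one always in the room (5.4) is coherent in itself. It does not satisfy a minimum of two monitoring throughout (3.1): if one therapist steps out, 5.4 is met and 3.1 is not. Only one of the pair has to be a clinician (5.1, 5.4). Under the one-present rule the person in the room may therefore be the other one, although 5.1 keeps a clinician available throughout.

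**3. Clearing discharge.** Sections 3.1 and 5.4 can be combined: the psychiatrist evaluates safety, and a named role judges that effects have resolved. But the V3 and V4 procedures do not list the psychiatrist's evaluation, and the schedule of events (6.2.1) has no row for it. The schedule's adverse event review with the side effect scale is not assigned to a psychiatrist. Staff can complete every listed V3 or V4 step and still omit what 3.1 requires. That is a lack of clarity and not a flat contradiction.

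**The case against.** **Is this only loose wording?** All the discharge texts wait for acute effects to resolve, no section calls its time a minimum stay, and section 5.4 is the one outlier against several mentions of 6 to 8 hours. All of that is correct, and it means that nobody is to be sent home while still affected. It does not settle whether a participant whose effects have resolved at 6 hours may leave.

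**Can a therapist alone discharge under 5.4?** A reader might infer this from the slashes. The text does not say that any one role is enough, and nothing in 5.4 waives the evaluation in 3.1. What stands is that the wording leaves the question open and that the visit procedures do not list the evaluation.

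**On-call or onsite psychiatrist?** Section 5.4 says "An on-call psychiatrist will be available at all times to further assess as needed for acute concerns", while the rescue medication text in 5.6 says "the participant will be managed under the care of the onsite psychiatrist". A reader might see a further contradiction. An on-call psychiatrist can be onsite, so the two are compatible. At most the wording needs clarifying.

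**Are adverse event counts not comparable between 10 mg and 25 mg?** A reader might infer this too. The documents do not support it: the discharge text for V3 and V4 is identical, and 5.4 covers both sessions. Section 7.2 plans only the percentage of each adverse effect. Events are collected from V1 to V9 (8.1), with specific questioning at each contact (8.2) and a further side effect rating at V5. An event after discharge can still be captured.

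**Can the 2 hours be summed over the trial?** Multiplying 20 participants by 2 sessions by 2 hours gives 80 hours. That total would require every session to end at exactly 6 hours, so it is a ceiling and says nothing about what is likely.

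**Conclusion.** The concern holds on two contradictions and one unclear rule. Earliest discharge is 8 hours in 5.4 and 6 hours in 6.1.2.1. Therapists present throughout number at least two in 3.1 and one, or at least one, elsewhere. The psychiatrist's evaluation required by 3.1 is not listed in the procedures that staff follow on the day.

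The size is up to 2 hours of directly observed time per session and one set of vital signs. This assumes that 5.4 is read as no discharge before 8 hours and that vital signs continue at 1.5-hour intervals until discharge. The time after typical resolution, 0-1 hour against 2-3 hours, also treats the 5 to 6 hours in 5.4 as the end of effects. The protocol offers that only as the usual course, and individual discharge still waits for resolution.

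The consequence is inconsistent supervision and avoidable deviations. The adverse event endpoint is not invalid, because it covers the whole trial and does not depend on discharge time alone. The correction is worth making because the rules protect participants directly.

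**What to change.** Reconcile sections 3.1, 5.2, 5.4 and 6.1.2.1 to one governing statement each for:
- the time of discharge, and whether it is a fixed time, a minimum or a range;
- the number of therapists present during the session, as distinct from the number assigned;
- who evaluates the participant before discharge and who clears it, with that step entered in the V3 and V4 procedures and in the schedule of events.

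Let every other section refer to these statements. Add the actual discharge time to the case report form for V3 and V4. The visit procedures do not now ask for it, and it would allow directly observed acute events to be described over a known interval. The on-call and onsite wording can be clarified in the same amendment. Which rule is adopted in each case is for the investigators.

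The cost is a wording amendment with ethics board approval (section 12.1) and one added data item per session. Any extra staff time depends on the rules chosen: a later discharge could add up to 2 hours per session. The time needed for continuous presence of two therapists or for a psychiatrist's evaluation cannot be estimated from the protocol.

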## **5.5 Participant Compliance Monitoring**

The IP will be administered to the participant in front of study personnel. Thus, administration of the IP will be supervised by study personnel to ensure compliance.

## **5.6 Concomitant Therapy**

All prescription and non-prescription medications (e.g. over-the-counter drugs and herbal supplements) that participants report taking during the 30 days prior to Screening (V1) will be assessed and recorded at V1. For each medication, documentation should list the trade or generic name, the total daily dose including units (or the dose, units, and scheduled and actual frequency of administration if the medication is not taken daily), the route of administration, and the reason for use. Where applicable, medication reports should be corroborated with participant medical records. All as-needed (*pro re nata*, PRN) prescriptions should be converted to reflect the actual number of pills or dose taken per day.

Concomitant medication refers to all drugs and therapies used from the time the ICF is signed through until the end of study participation. Changes, additions, or discontinuations to medications and/or therapy will be assessed, recorded, and verified with participants in the CRF during each study visit.

#### Permissible Medications

Medications for the management of concurrent anxiety and insomnia, or non-psychiatric medications that have a potential psychotropic effect are permitted within the following limitations.

For the initial Screening Visit (V1) through to the final study visit (V9), participants are permitted to use benzodiazepines (up to 2mg of lorazepam equivalent per day for insomnia and anxiety if it is not taken within 12 hours before both of psilocybin doses (V3 & V4). Prescription and nonprescription medications with psychoactive properties that are used as needed for non-psychiatric conditions (e.g. pseudoephedrine for allergies or cold, zolpidem/zopiclone for sleep disorders) should be used no more than 2 times a week and not within 12 hours before any study assessment. Documentation of the use of adjunctive anxiolytics, hypnotics, or medication with potential psychotropic properties (including over-the-counter preparations) will be obtained at each visit.

#### Permissible Contraceptive Methods

A woman/female or person who is not of childbearing potential is considered to be postmenopausal after at least 12 months without menstruation. The participant must be on a permissible contraceptive for a minimum of 3 months prior to screening and for the duration of the study. The following methods of contraception, if used properly and used for the duration of the study, are permissible:

- Combine estrogen-and progestogen-containing hormonal contraception associated with inhibition of ovulation:
  - Oral
  - Intravaginal
  - Transdermal
- Progestogen-only hormonal contraception associated with inhibition of ovulation:
  - Oral
  - Injectable
  - Implantable
- Intrauterine device
- Intrauterine hormone-releasing system
- Bilateral tubal occlusion
- Vasectomized partner
- Sexual abstinence
- Tubal ligation/ occlusion

Periodic abstinence (e.g. calendar, symptothermal, or postovulation methods) is not an acceptable form of contraception for this study.

These methods of contraception also apply to partners of male participants.

The investigator (or delegate) and each participant will determine the appropriate method of contraception for the participant during the participation in the study. This will be documented at Screening (V1).

### Prohibited Medications

Participants are to be discontinued from antidepressants and/or antipsychotic medications at least 2 weeks prior to Baseline (V2). Participants on fluoxetine will be tapered off the medication at least 4-weeks prior to Baseline (V2). Additional time may be required as determined by the study investigator. Medications that must be discontinued include the following 2 classes of the Anatomical Therapeutic Chemical (ATC) Classification System: NO5A Antipsychotics & NO6A Antidepressants. Methylphenidate is also included in this list.

These medications should not be re-introduced until after Week 12 (V9) when the study is complete. If the medications are re-introduced, the study investigator must be notified and the medications will be documented in the participant's CRF. Participants who require concomitant medication(s) specifically for the treatment of depression at any time through the duration of the study will be assessed for reasons of resuming their medications.

